## Research Question and Aims

Hypothesis: A pre-ICU simulation session will decrease the incidence and severity of post-operative delirium in the ICU after an elective cardiothoracic surgical procedure.

Aims, purpose, or objectives: The purpose of this project is to evaluate the effect of a pre-ICU admission simulation session on post-operative delirium in the elective cardiothoracic surgical population,

Background (*Include relevant experience, gaps in current knowledge, preliminary data, etc.*):

Cardiothoracic patients are at a high risk for post-operative delirium in the intensive care unit (ICU). Approximately 50% of patients admitted to the intensive care unit develop or are impacted by some form of acute delirium. This can lead to a three-fold increase in 6-month mortality, increased time on the mechanical ventilator, elongated hospital length of stay, and nearly 50% of those patients affected having a cognitive impairment at hospital discharge some with long term cognitive impairment (approximately 1 in 3 patients). Specifically, delirium incidence in the post-cardiac surgery population is between 26-52%. Delirium in this population specifically has been associated with increased mortality, stroke risk, hospital readmission and cognitive dysfunction as well as poorer functional status.

The literature supports the use of pre-operative educational experiences as a mechanism to reduce delirium incidence.

The initial phase of this project is to identify the baseline rate of delirium in the cardiothoracic surgical intensive care unit. Anecdotal data from practitioners in this unit indicate that post-operative delirium across “surgical procedure types” is a strong concern. A primary gap in this population’s care is that our institution does not have a program in place to prepare patients for the experience they will have admitted to the ICU post-operatively.

The initial phase of this project will include baseline data collection over a period of 3 months to determine current delirium rates (CAM-ICU) and other ICU outcome metrics including ventilator time, use of sedatives and antipsychotics, restraint use rates, and ICU and hospital length of stay.

Following initial baseline data collection, the intervention will be to provide a pre-cardiothoracic surgery patient a multi-sensory pre-recorded virtual reality ICU simulation experience to introduce them to the senses they can

expect to encounter post-operatively when admitted to the critical care unit. This is intended as a mechanism to reduce post-operative delirium in this population by allowing them to “become familiar” with the sights/sounds/tactile experiences in the ICU so that they are not completely foreign to the patient upon admission post-operatively.

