## Study Design and Methods

**Methods:** *Describe in lay terms, completely detailing the research activities that will be conducted by Mayo Clinic staff under this protocol.*

Data collection and Outcome Metrics :

- CAM-ICU scores in the post-operative setting
- Incidence of acute delirium in the post-operative setting
- Time of intravenous sedation in the post-operative setting
- Time of mechanical ventilator in the post-operative setting
- Incidence of anti-psychotic medication administration to treat delirium
- Incidence and duration of cardiopulmonary bypass “pump time”
- Metrics will be stratified based on type of operative procedure, operative time, age, gender, necessity for return to operating room prior to initial extubation

The data source will be the electronic medical record. Baseline retrospective data will be collected on patients prior recorded prior to the start date of this IRB submission; prospective patients undergoing simulation session will have data recorded post IRB start date. Data collection form attached with IRB submission.

Charts of all initial post cardiac surgery patients admitted directly to the ICU who meet the above criteria will be reviewed.

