### **Subject Information**

*Target accrual is the proposed total number of subjects to be included in this study at Mayo Clinic. A “Subject” may include medical records, images, or specimens generated at Mayo Clinic and/or received from external sources.*

Target accrual: 50 historic patients for baseline metric; 50 current intervention patients to undergo simulation session.

Subject population (children, adults, groups): Adult

Inclusion Criteria: Baseline normal neurological function pre-operatively, planned use of mechanical ventilator with endotracheal tube post-operatively after planned cardiothoracic surgical procedure. Age: greater than 18 and less than 60.

**Exclusion Criteria:** Chronic dementia, Alzheimer's disease, or other chronic neurological disease (i.e. Bi-Polar). Chronic use of neurological altering medications such as benzodiazepines, psychotropic, anti-depressants, anxiolytics. Patient undergoing emergent surgery. Use of post-operative cardiopulmonary support devices such as ECMO (extracorporeal membrane oxygenation), intra-aortic balloon pump, total artificial heart, or other similar device. Age greater than 60; Age less than 18. Previous admission to an intensive care unit (intervention patients).

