### Data Analysis

*Power analyses may not be appropriate if this is a feasibility or pilot study, but end-point analysis plans are always appropriate even if only exploratory. Provide all information requested below, or provide justification if not including all of the information.*

**Power Statement:** Based on the literature indicating incidence of post-operative delirium in the post cardiothoracic surgical population and initial power analysis calculations, initial calculations indicate sample size of approximately 30 patients. Therefore, to accommodate for patient loss to follow-up will aim for sample size of 50 patients.

**Data Analysis Plan:** A comparative analysis of the outcome metrics described in the "Study Design and Methods" section will be completed between the pre-implementation baseline data and the post-implementation intervention data. This analysis will evaluate the effect of the multi-sensory ICU simulation experience on post-operative delirium in the cardiac surgical population. An additional post-implementation interview/survey will be conducted on post-intervention patients as described above.

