### Endpoints

**Primary:** Study to end when sample sizes are obtained.

**Secondary:** None.

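### Must restraint use and length of stay be added to the compared outcomes, and a severity measure be named?

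*Protocol*

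**What the plan says.** The hypothesis in Research Question and Aims is that the simulation session "will decrease the incidence and severity of post-operative delirium in the ICU". The Background in the same section describes an initial phase of baseline data collection "to determine current delirium rates (CAM-ICU) and other ICU outcome metrics": ventilator time, sedatives, antipsychotics, and finally "restraint use rates, and ICU and hospital length of stay".

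Study Design and Methods gives the list of data items and outcomes. It opens with "CAM-ICU scores in the post-operative setting", gives delirium incidence a separate entry, and goes on to sedation time, ventilator time, antipsychotic administration, and bypass use and duration. It takes all data from the electronic medical record and adds: "Data collection form attached with IRB submission". That form is not shown.

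Subject Information sets the groups: "50 historic patients for baseline metric; 50 current intervention patients to undergo simulation session". The Data Analysis Plan promises "A comparative analysis of the outcome metrics described in the" Study Design and Methods section. Endpoints has "Secondary: None", and its primary entry only says when the study closes.

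**The concern.** The only comparator is a historical group. A metric collected at baseline can therefore inform the effect of the simulation only if it is also collected and compared in intervention patients. Three quantities are called outcome metrics for the baseline phase and then drop out of the list that defines the comparison. The Background itself gives longer hospital stay as a consequence of delirium, so these do not look like incidental fields.

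The word severity appears once, in the hypothesis, and no measure is attached to it. The baseline data are retrospective, so control outcomes already exist when a measure is chosen. An analyst could in principle settle on worst score, number of positive days, antipsychotic use or sedation time after seeing the results. Half of the hypothesis might then be judged on a measure picked for its answer.

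**Working it through.** No figure in the Protocol bears on this point, so the check compares the lists.

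**Baseline metrics in the Background against the Study Design and Methods list**

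| Background | Study Design and Methods |
|---|---|
| Delirium rate (CAM-ICU) | CAM-ICU scores; delirium incidence |
| Ventilator time | Listed |
| Sedative use | Listed, as time on intravenous sedation |
| Antipsychotic use | Listed, as incidence |
| Restraint use | Absent |
| ICU stay | Absent |
| Hospital stay | Absent |

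Four of seven carry over and 7 − 4 = 3 do not. Bypass use and duration appear only in the Study Design and Methods list.

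**Is this a contradiction?** The Background sentence sets out what a preliminary phase will describe about the unit. The Data Analysis Plan sets out what will be compared. The second set may be smaller than the first without conflict: a study may describe more at baseline than it tests. A contradiction would need one place to promise a comparison that another rules out, and no such promise is made for the three metrics. The hypothesis, the aim and the Data Analysis Plan all frame the question as an effect on delirium.

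**Does the Endpoints section exclude them?** Its primary entry is a closing condition, not an outcome, so the section was evidently not completed as an outcome hierarchy. Read literally, the secondary entry would also deny secondary status to sedation time and ventilator time, which the Data Analysis Plan does compare. It is weak evidence about the three metrics.

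**Severity.** The hypothesis has two parts, incidence and severity. The Study Design and Methods list has two delirium entries, CAM-ICU scores and incidence. The natural pairing is one entry per part; otherwise the first entry would be redundant. The CAM-ICU mention beside delirium rates in the Background does not exclude using the scores as well. What is unstated is the summary of the scores.

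**What would adding the three metrics gain?** With all 50 patients per group analysed, the 95% half-width for a difference in proportions is 1.96 × √(2 × 0.25/50) = 0.196. This takes 0.5 in both groups as the widest case, because no restraint rate is given. For a difference in means it is 1.96 × √(2/50) = 0.39 SD. The target of 50 allows for losses from about 30. If only 30 intervention patients remained against 50 historic (an assumption), the half-widths become 1.96 × √(0.25/30 + 0.25/50) = 0.226 and 1.96 × √(1/30 + 1/50) = 0.45 SD. The SD figures also presume a comparison of mean stays, and the Protocol gives no distribution for stay. These widths show that the extra comparisons would be imprecise. They do not measure the seriousness of a list mismatch.

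**The case for a change.** The best case for a change is that the Background sentence is prospective and calls the items outcome metrics, so it is a plan statement and not mere context. An analysis plan can supply methods, but it does not by itself align two lists inside the Protocol. The data collection form may hold the three fields, yet the comparison is defined by the Study Design and Methods section and not by the form. A single sentence would settle what severity means, at almost no cost, and the existing control data make it worth fixing in advance.

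Part of this stands. The lists do differ, the linking phrase for severity is missing, and some freedom in summarising CAM-ICU scores remains. The step from there to a needed change does not stand. Adding restraint use and stay as secondary outcomes goes beyond the stated question and is largely a preference. It would also put more comparisons into a small historical-control study whose Endpoints section names no primary outcome, which raises the risk of selective reporting. Counting CAM-ICU-positive days would measure duration or burden, so it would fit the hypothesis only if the hypothesis were reworded.

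**Conclusion.** No change follows. The mismatch is real but small: 3 of 7 baseline metrics are not carried into the compared list, and one of the two parts of the hypothesis lacks an explicit label for its measure. The first is a description wider than the comparison. The second is a gap that an analyst would sensibly fill from the CAM-ICU entry. Neither affects the delirium-incidence comparison, which has its own entry in the list.

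This rests on three readings: that the Background sentence describes the unit and promises no test; that CAM-ICU scores, listed apart from incidence, are meant for severity; and that their summary is fixed in an analysis plan, which may exist but was not available. If the second reading were wrong, the severity half of the hypothesis would lack a measure, but the incidence half would be unaffected.

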## Study Design and Methods

**Methods:** *Describe in lay terms, completely detailing the research activities that will be conducted by Mayo Clinic staff under this protocol.*

Data collection and Outcome Metrics :

- CAM-ICU scores in the post-operative setting
- Incidence of acute delirium in the post-operative setting
- Time of intravenous sedation in the post-operative setting
- Time of mechanical ventilator in the post-operative setting
- Incidence of anti-psychotic medication administration to treat delirium
- Incidence and duration of cardiopulmonary bypass “pump time”
- Metrics will be stratified based on type of operative procedure, operative time, age, gender, necessity for return to operating room prior to initial extubation

The data source will be the electronic medical record. Baseline retrospective data will be collected on patients prior recorded prior to the start date of this IRB submission; prospective patients undergoing simulation session will have data recorded post IRB start date. Data collection form attached with IRB submission.

Charts of all initial post cardiac surgery patients admitted directly to the ICU who meet the above criteria will be reviewed.

### Pre ICU Simulation Survey – Patient

1. You are going to be admitted to the intensive care unit after your surgery. What are your thoughts / feelings / fears regarding your upcoming ICU stay?

Post-ICU Simulation, intervention patients will be surveyed with the following questions:

1. What was the biggest take-home point you learned during your virtual reality ICU simulation experience?
2. How do you hope that this ICU simulation experience will impact your actual ICU experience after your cardiac surgery?

Post actual ICU experience, intervention patients will be surveyed in person with the following questions:

1. Please describe your ICU experience.

2. What do you remember from your virtual reality pre-operative ICU simulation experience?
3. Did you experience any of the things you experienced in the virtual reality ICU simulation during your actual ICU experience? Please describe.
4. How do you feel that your pre-operative virtual reality ICU simulation experience impacted your or prepared you for your actual ICU experience?
5. Did you feel that the pre-operative virtual reality ICU simulation experience was beneficial?
6. What about your actual ICU experience was unfamiliar to you?
7. How would you modify the pre-operative virtual reality ICU simulation experience to improve your actual ICU experience?

Informed consent for research will be obtained by a member of the research team in the pre-surgical clinic setting; a future date for the simulation session will then be mutually agreed upon by study staff and patient/family.

Following informed consent for research, the pre-surgical patient will be asked to view a 10 minutes pre-recorded virtual reality simulation session from the perspective of a postoperative ICU patient. This virtual reality simulation session has been recorded in the Mayo Clinic Simulation Center under the guidance of study team members from Critical Care, and Cardiothoracic surgery.

The multi-sensory ICU simulation experience will include the following:

- View on a virtual reality head set
- Introduce to different care team members
- Introduction to common equipment found in the patient room in the intensive care unit
- Introduction to common experiences, sounds, sights and procedures in the intensive care unit
- Total video duration: 10 minutes

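### Intervention patients enter only through the pre-surgical clinic, but historic charts carry no such condition, so non-emergent in-hospital cases may enter the historic group alone

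*Protocol*

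**What the plan says.** **Intervention group.** Under Pre ICU Simulation Survey – Patient, the protocol says "Informed consent for research will be obtained by a member of the research team in the pre-surgical clinic setting", and that "a future date for the simulation session will then be mutually agreed upon by study staff and patient/family". No other route of entry is described and no minimum interval before surgery is set.

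**Historic group.** Under Study Design and Methods: "Baseline retrospective data will be collected on patients prior recorded prior to the start date of this IRB submission". Selection is by chart: "Charts of all initial post cardiac surgery patients admitted directly to the ICU who meet the above criteria will be reviewed". Neither sentence mentions a clinic visit or the type of admission.

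**Criteria for both groups.** Subject Information requires "planned use of mechanical ventilator with endotracheal tube post-operatively after planned cardiothoracic surgical procedure" and lists "Patient undergoing emergent surgery" among the exclusions. The only criterion expressly confined to one group is previous ICU admission, which excludes intervention patients.

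**Target population.** Research Question and Aims states the hypothesis for "post-operative delirium in the ICU after an elective cardiothoracic surgical procedure" and the aim for "post-operative delirium in the elective cardiothoracic surgical population".

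**Analysis.** Data Analysis compares the baseline data with the intervention data. Study Design and Methods lists as stratifying factors the kind of procedure, its length, age, gender and an early return to theatre.

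**The concern.** The two groups of 50 are compared without randomisation, so any difference in case mix that comes from how patients were found will be read as an effect of the simulation. The clinic route selects patients who are at home, or at least outpatients, when they are recruited. The chart route does not. If some historic patients were already in hospital when their operation was planned, the historic group contains a kind of patient that the intervention group cannot contain under the stated consent route.

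Stratification cannot repair this as listed, because no factor describes urgency or admission route. Adding such a factor at the analysis stage would help only in part: a stratum made up solely of historic patients has no intervention patients to compare with, so it would have to be dropped. The question therefore belongs to the definition of the cohorts.

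**Working it through.** **1. Entry conditions side by side**

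| Condition | Intervention | Historic |
|---|---|---|
| Planned procedure | required | required |
| Emergent surgery | excluded | excluded |
| The word *elective* in the criteria | absent | absent |
| Consent in the pre-surgical clinic | required | no equivalent |
| Session on a later date before surgery | required, no minimum interval | no equivalent |
| First post-surgical, direct ICU admission | not stated separately | required |

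The chart-review sentence refers to criteria stated above it. I take these to be the ones under Subject Information, the only criteria in the protocol. I read direct admission to the ICU as where the patient goes after surgery; it does not say where the patient was beforehand.

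**2. Test case.** Take a patient in hospital whose operation is scheduled during that stay and is not emergent.

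- Historic group: eligible if *planned* is read to include an operation scheduled during an existing admission; not eligible if *planned* is read as *elective*. The criteria do not settle this, and two chart reviewers could decide differently.
- Intervention group: no route in, because consent is taken in the pre-surgical clinic.

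The groups are aligned on the narrow reading of *planned* and not on the wide one.

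**3. Illustration of size.** The protocol gives no share of in-hospital cases and no risk for them, so everything here is assumed except the 26–52% delirium range in Research Question and Aims and the 50 per group in Subject Information.

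Let p be the delirium rate in clinic-route patients, s the share of in-hospital cases in the historic group only, and r their risk relative to p. With no true effect:

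historic rate = (1 − s)·p + s·p·r, so spurious difference d = p·s·(r − 1).

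With p = 30%, which lies inside the protocol's range:

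- s = 0.2, r = 1.5: 0.8 × 0.30 + 0.2 × 0.45 = 0.33, so d = 3 points
- s = 0.2, r = 2: 0.8 × 0.30 + 0.2 × 0.60 = 0.36, so d = 6 points
- s = 0.3, r = 2: 0.7 × 0.30 + 0.3 × 0.60 = 0.39, so d = 9 points

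At the ends of the protocol's range, with s from 0.1 to 0.4 and r from 1.5 to 1.9:

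- p = 26%: d runs from 0.26 × 0.1 × 0.5 = 1.3 points to 0.26 × 0.4 × 0.9 = 9.4 points
- p = 52%: d runs from 0.52 × 0.1 × 0.5 = 2.6 points to 0.52 × 0.4 × 0.9 = 18.7 points

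The chance of a significant false benefit (normal approximation, two-sided 5%, counted in the favourable direction) is Φ((d − 1.96·SE₀)/SE₁), with SE₀ pooled and SE₁ unpooled at 50 per group. It rises from the nominal 2.5% to between 3.5% and 17% for p = 26%, and to between 4.5% and 49% for p = 52%.

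If s = 0 or r = 1, then d = 0. If r is below 1, d changes sign.

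**The case against.** The strongest reply is that the protocol already describes an elective population. The hypothesis and aims say so, the procedure must be planned, and emergent surgery is excluded in both groups. Read together, the natural meaning is that historic charts are elective as well, and then this source contributes no bias. This largely stands. A reader might infer that urgent in-hospital cases will enter the control group; the documents do not support that. They support only that such cases may enter, because chart screening applies the criteria, and the criteria use a different word from the hypothesis.

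A reader might also infer that a patient seen in clinic shortly before surgery could be a control but not an intervention patient. The text gives no basis for this: there is no minimum interval, the video lasts 10 minutes, and nothing prevents a session the next day.

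Nor do the documents support saying that the bias favours the simulation. That depends on in-hospital cases having a higher delirium risk, which is an assumption. The other criteria (under 60, normal neurological function, no chronic psychotropic medication, no post-operative mechanical support) plausibly remove some of the sicker patients. With 50 per group at 30%, the standard error of the difference is √(2 × 0.3 × 0.7 / 50) = 9.2 points, so a shift of 3 to 6 points is less than one standard error.

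Finally, the data collection form is not shown and may record admission type or dates, and a statistical analysis plan may adjust for them. That is possible, but it does not settle which charts qualify as controls, which is for the protocol to decide.

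**Conclusion.** The point holds in a limited form. The intervention group has a clinic-route condition that the historic group lacks, and the criteria do not enforce the elective population named in the hypothesis. Non-emergent operations planned during an existing admission may therefore enter the historic group and not the intervention group, and no listed stratifying factor would reveal it.

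The size and direction of any bias are unknown from the document and could be zero. The illustrative shifts, from 1.3 to 18.7 points, rest wholly on assumed shares and risk ratios and show only what would be at stake. This is a worthwhile and inexpensive tightening of cohort definition, not a demonstrated bias.

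**What to change.** - In Study Design and Methods and in Subject Information, limit both cohorts to elective procedures, so that the criteria use the same term as the hypothesis.
- In Study Design and Methods, limit historic charts to patients with a documented pre-surgical clinic visit before the index admission.
- Record admission type, clinic date and surgery date in both cohorts.
- If a minimum clinic-to-surgery interval is wanted, set it in advance and apply it to both cohorts. It should not be derived from intervals observed in the intervention group: baseline data are collected first, so those intervals are not known at chart screening, and an observed minimum would rest on one extreme patient.

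**Cost.** One added screening rule and a few fields on the collection form, if they are not already there. Some historic charts will be lost, and the look-back may need to be somewhat longer than the 3 months given in Research Question and Aims to reach 50. A longer look-back also widens the calendar gap between the cohorts, so it should be extended no further than needed.

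### Only the intervention group passes a volunteer step, so any difference in delirium risk between volunteers and other eligible patients is mixed into the estimated simulation effect, in an unknown direction

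*Protocol*

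**What the plan says.** **Intervention group.** The section with the patient survey states that "Informed consent for research will be obtained by a member of the research team in the pre-surgical clinic setting" and that "a future date for the simulation session will then be mutually agreed upon by study staff and patient/family". These patients are also surveyed before the session, after it, and after the ICU stay.

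**Historic group.** Study Design and Methods says "Baseline retrospective data will be collected on patients prior recorded prior to the start date of this IRB submission". For prospective patients, the same section describes data recording only for those who go through the session. It then adds: "Charts of all initial post cardiac surgery patients admitted directly to the ICU who meet the above criteria will be reviewed". That sentence is not tied to either period.

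**Numbers.** Subject Information sets "50 historic patients for baseline metric; 50 current intervention patients to undergo simulation session". It does not say how the 50 historic patients are drawn. It also excludes patients with a prior ICU stay, but for the intervention group only.

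**Comparison.** The Data Analysis Plan compares outcomes "between the pre-implementation baseline data and the post-implementation intervention data" and concludes: "This analysis will evaluate the effect of the multi-sensory ICU simulation experience on post-operative delirium in the cardiac surgical population". The only named control for group differences is stratification by procedure type, length of operation, age, gender and early return to the operating room.

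**The concern.** A patient reaches the intervention group only by being approached in clinic, agreeing to research, settling a date and attending. A historic patient needs only a chart that meets the criteria. The filter acts on one side and would act within any calendar period, so matching periods or clinic routes would not remove it.

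Volunteers may differ from other eligible patients in anxiety, support at home, frailty or time available before surgery. None of the listed strata measures these. If any of them is related to delirium, the comparison will show a difference even when the session does nothing, or will hide one when it works.

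The protocol provides for no data on eligible intervention-period patients who decline, are not approached or do not attend. As written, the study would hold nothing with which to tell selection from effect.

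**Working it through.** The plan gives no figure of its own for this selection, so there is none to reproduce. The sample-size statement does not bear on the point.

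**Inputs**
- Delirium among all eligible patients, p = 39%: the midpoint of the 26-52% given in the Background, (26 + 52)/2.
- Consent fraction f: not in the protocol; assumed.
- Decliner-to-volunteer risk ratio r: not in the protocol; assumed, on both sides of 1.
- No true effect of the session. The 50 historic patients are taken to represent the eligible patients of their period.

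**Step 1. Volunteer rate under no effect.** Since p = f·v + (1 − f)·r·v, the volunteer rate is v = p/(f + (1 − f)·r). With f = 0.5:
- r = 0.8: 0.39/0.90 = 43.3%, a spurious rise of 4.3 points
- r = 1.25: 0.39/1.125 = 34.7%, a spurious fall of 4.3 points
- r = 1.5: 0.39/1.25 = 31.2%, a spurious fall of 7.8 points
- r = 2: 0.39/1.5 = 26.0%, a spurious fall of 13.0 points

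**Step 2. Sensitivity to uptake** (change in points, participants minus historic):

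| f | r = 0.8 | r = 1.25 | r = 1.5 | r = 2 |
|---|---|---|---|---|
| 0.3 | +6.3 | −5.8 | −10.1 | −16.1 |
| 0.5 | +4.3 | −4.3 | −7.8 | −13.0 |
| 0.7 | +2.5 | −2.7 | −5.1 | −9.0 |
| 0.9 | +0.8 | −1.0 | −1.9 | −3.5 |

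**Step 3. Chance of a false positive.** This uses a pooled two-proportion z-test, 50 v 50, two-sided 5% (the protocol names no test, so this is also an assumption). At 39%, with f from 0.4 to 0.8 and r from 1.25 to 2, the chance of a significant result favouring the simulation is 3.8% to 35%, against a nominal 2.5%. A middle case, f = 0.6 and r = 1.5, gives 0.39/1.2 = 32.5%, a 6.5-point spurious fall and a chance of about 10%.

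**Step 4. Which comparison detects pure selection?** Take f = 0.5 and r = 1.5 with no effect:
- historic: 39.0%
- participants: 31.2%
- concurrent non-participants: 1.5 × 31.2 = 46.8%
- all eligible after the start: 0.5 × 31.2 + 0.5 × 46.8 = 39.0%

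The all-eligible comparison is 39% v 39% and correctly shows nothing. Non-participants above the historic rate are the mark of selection.

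**Step 5. What that comparison costs in precision.** With half participating, a true fall of d points among participants appears as d/2 overall. If 50 participants imply 50/0.5 = 100 eligible patients after the start, against 50 historic, the standard error is √(0.39 × 0.61 × (1/50 + 1/100)) = √0.00714 = 0.0845. The 95% half-width is 1.96 × 0.0845, about 17 points.

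**The case against.** **An open design choice.** The protocol plainly describes a non-randomised before-after study, and nothing quoted contradicts itself. Sensitivity analyses often belong in an SAP, which is not shown. This stands in part: it would be too strong to say that no analysis could ever reveal the problem. But the protocol determines whose records are abstracted, and an SAP cannot analyse non-participants whose data are not collected.

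**Unknown direction.** A reader might infer that the design favours the simulation. The documents do not support that. Patients who fear the ICU could be keener to accept a preparation session, in which case r is below 1 and a real benefit would be masked. This stands, and the range above therefore covers both directions.

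**Possibly small.** The session is a 10-minute video, so uptake could be high; at f = 0.9 and r = 1.25 to 1.5 the distortion is only 1 to 2 points. Eligibility is limited to adults under 60 having planned surgery, with normal baseline neurological function and no chronic psychoactive medication. This narrows the room for a ratio as large as 2. The strata may also absorb selection that runs through age, gender or procedure. All of this reduces the concern without removing it.

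**Readings that go too far.** A reader might infer that the historic group was entered without consent, or that it contains everyone eligible. The protocol states neither. No waiver is described, the historic number is fixed at 50, and the method of drawing them is not given. What the text does support is that records predating the submission cannot have passed the clinic consent step described for the session. Nor are the historic patients unselected, since they must meet the eligibility criteria.

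**Are non-participants already covered?** The sentence on reviewing all qualifying charts could be read that way. The more specific sentence limits prospective data to those who undergo the session, and the analysis plan makes no use of anyone else.

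**Conclusion.** The point holds as a one-sided volunteer filter whose effect the plan attributes to the simulation. Its size and direction are unknown. At 39% overall, with half consenting and r between 0.8 and 2, the distortion runs from a 4-point spurious rise to a 13-point spurious fall. It shrinks as uptake rises and vanishes at r = 1. Only the 26-52% range comes from the protocol; the uptake and the ratio are assumptions.

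This does not show that a favourable result would be false. It shows that the planned comparison cannot separate the session from the kind of patient who agrees to it. The period difference and the one-sided prior-ICU exclusion are separate sources of non-comparability that add to this one. The improvement is worth making because it is cheap, and permission to abstract non-participants' records is easier to obtain in advance.

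**What to change.** **Study Design and Methods.** State that the chart review also covers every eligible intervention-period patient who declined, was not approached or did not attend, using the same data collection form. Confirm that the chart-review permission extends to them; nothing in the present text grants this.

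**Data Analysis.** Report delirium for three groups: historic eligible patients, concurrent eligible non-participants, and participants. Add a comparison of all eligible patients before with all eligible patients after the start. Apply the prior-ICU-admission criterion identically in both periods; otherwise eligible means different things on the two sides.

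**Interpretation.** Attribute a fall to the simulation only if the all-eligible comparison also falls. Read a non-participant rate above the historic rate as a sign of selection. Otherwise word the result as an association. It is tempting to claim an effect whenever participants fall and non-participants do not move to the same extent, but that rule should not be used. In Step 4 participants fall 7.8 points and non-participants rise 7.8 with no effect at all, so the rule passes pure selection. A fall in the all-eligible comparison is necessary but not sufficient, since other changes over calendar time could also produce it.

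**Cost.** Additional abstraction, permission wording and no patient contact. The all-eligible comparison is diluted by non-participants and imprecise at this size (about ±17 points under the assumptions of Step 5). It can temper the conclusion but will rarely settle it.
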